Aim 2: Evaluate the proposed T-CAP measures to assess their performance in gauging the impact of telehealth on initiation of in-person Substance Use (SU) treatment, short-term retention in referred SU treatment, and access to other appropriate treatment services (e.g., MAT). Our multidimensional approach includes data from self-report attendance and treatment engagement, self-report drug use, Coaches' advocate records on number of completed assertive referrals, and agency records from police and BH providers (including intake and during-program UA test results). In order to examine groups differences for intervention completers (C) vs non-completers (NC) (i.e., individuals who do not complete the 7 coaching video calls), group differences using t-tests and chi-square tests and we will estimate effect sizes needed for determining a sample size for a future R01 proposal. To assess potential assignment bias, we will test to see if there are baseline differences in demographics: participant race, gender, age and other demographic characteristics, as well as baseline measures of opioid use frequency and amount will be examined using chi-square and t-tests. Effect sizes will be computed for group differences on multiple outcomes (treatment initiation, retention, referrals to expanded SU service options, missed appointments). Service attendance records will be corroborated monthly with service provider records. Examinations of referrals to MAT and alternative pain management care between the C and NC groups, utilizing agency records data and the Coach tracking, will be conducted using a z-score to test differences in proportions of referral types. This will be calculated for all assertive referrals (resulting in scheduled appointments) collectively for a participant, as well as for different types of services.

Analyses of Secondary outcomes. We will examine differences between C and NC groups on several secondary outcomes. Analyses will typically involve t-tests, chi-square tests, and correlations. For example, we will use t-tests to assess differences between groups on the 3-month follow-up measures

of treatment motivation and psychosocial function from the TCU Client Evaluation of Self and Treatment (TCU CEST), a widely used form listed on the IBR web page. Validation of recent (last few days) self-reported opioid use will be compared with drug testing outcomes at each assessment time point using McNemar's test for change of state, as well as computing sensitivity and specificity statistics and the kappa statistic as a measure of agreement. We will compare self-report, as well as urinalysis (UA) results from agency drug screens between the two groups.

15. Potential Risks and Precautions to Reduce Risk: Indicate any physical, psychological, social, or privacy risk which the subject may incur. Risk(s) must be specified. Also describe what measures have been or will be taken to prevent and minimize each of the risks identified. If any deception is to be used, describe it in detail and the plans for debriefing.

Breach of confidentiality. This risk will be minimized with procedures to safeguard the confidentiality of participants include assigning Research ID's to subjects. This number will be used as an identifier for all study materials including the participant's responses to the surveys, data stored from existing records, qualitative data, and T-CAP telehealth session data. Data from the T-CAP telehealth app will be stripped of participant phone number by the Project Coordinator, and the Research ID will be entered into the dataset. Participants will only be identified using this number and data will be reported in aggregate only. Consent forms with participant study numbers will be kept in a locked filing cabinet in a locked room in the IBR offices, accessible by authorized researchers. Electronic research data will be encrypted and password protected. Participants will be made aware during the consent process and prior to every research session that all information provided is considered to be confidential. Further procedures to protect confidentiality are described below. Only authorized research staff will have access to the de-identified data. Only the PI and Project Coordinator will have access to the T-CAP app data with the phone number when it is downloaded to the IBR secure server. These same authorized researchers will also have access to qualitative interview data, behavioral healthcare provider data, Qualtrics survey data with Research ID, and case notes from the Coaches. The RA will use the Research ID for reporting scheduling information (electronic files and demographic forms) to the IBR research team, and the Coach will use the Research ID when reporting case notes to the research team (electronic and paper files).

Coercion. While both the ODP participation and T-CAP participation are completely voluntary, there is a risk of perceived coercion that clients in the police diversion program may experience. This risk will be minimized in several ways. Participants will be informed that participation in this study will not in any way affect their status in the ODP. Further, ODP staff and officers will not be actively included as part of the study and will not be given feedback about any participant or any progress they have made in the study. Before the full rollout of the study, we will conduct presentations with ODP leadership and Lake County Health Department staff, and other stakeholders (e.g., community behavioral healthcare providers) to provide an overview of the study, and we will stress that study participation is voluntary and the participants may drop out of the study at any time if they wish.

Possible discomfort to study materials. Participants in the study will be asked to complete three survey batteries and seven telehealth sessions featuring MI with the Coach. Study participants may

experience some personal embarrassment or emotional discomfort from some of the survey questions or talking with the Coach. However, participants will be instructed that they can skip questions in surveys or during MI sessions that they do not feel comfortable answering.

16. Procedures to Maintain Confidentiality: Describe how the data will be collected, deidentified, stored, used, and disposed to protect confidentiality. If protected health information is to be re-identified at a later date, describe the procedure for doing so. All signed consents and hard data must be stored for a minimum of 3 years in a locked filing cabinet (and locked room) in the principal investigator's office, lab, or storage closet at TCU. Your professional society may recommend keeping the materials for a longer period of time.

Data from five sources will be subject to confidentiality procedure: (1) Qualtrics Surveys at baseline, 6 weeks and 12 weeks, (2) data from telehealth sessions, (3) data from Coaches, (4) data from community behavioral health providers, and (5) qualitative data from participant interviews.

The first step in maintaining confidentiality is to assign each participant an arbitrary Research ID that will be used on all data for that participant. A Master Link File will be maintained by the PI, Project Coordinator, Coaches and the field RA that will include the participant's name, Research ID, and study phone number. Treatment Code (described below) will only be included in the Master Link File maintained by the PI and Project Coordinator. This file will be encrypted and stored at the IBR on a secure computer separate from any other participant data. The Master Link File will be password protected, stored electronically, and kept separate from all other data files. It will be accessible only to authorized project staff.

Surveys. The RA will need to have the Master Link File on their TCU-owned secure laptop computer for tracking participants and obtaining Research IDs to enter on project materials. The laptop will be protected by a strong password and the link file, a Microsoft Excel database, will be encrypted and protected by a strong password. Every time a participant comes to complete a survey battery, the RA will use the participant name to look up the Research ID in the database. This will bring up the name and Research ID for that participant. The RA will enter the Research ID on the Qualtrics survey battery or on the paper version alternative. Updated Master Link Files will be uploaded by the RA via TCU Box for download by the IBR authorized researchers (PI or Project Coordinator). Master Link Files will not be stored in a TCU Box folder.

The RA will instruct the participant not to put their name or other identifying information on any paper forms. The Demographics Form—completed only at baseline—includes questions on demographics and background information, and does not have any questions of a sensitive nature. When the participant returns the Demographics Form, it will be mailed to the IBR in an envelope with the Contact Information Form. In the event that the Baseline battery of assessments is completed on paper (this is a back-up option in the event that internet access is not functioning), the survey will be mailed to the IBR in a FedEx envelope, separate from the Demographics Form and Contact Information Form. Data collection on Qualtrics will not have other data that could be used to identify the participant. When

surveys are completed using Qualtrics, the resulting data file is not readable until it is uploaded to the secure Qualtrics server on the TCU campus.

Telehealth session data. The 2-question telehealth satisfaction survey completed on a smart phone at the end of each telehealth session will be available for download through the TCAP app to TCU Box, accessible only by the PI and Project Coordinator. The data will be linked to the phone number and will not include any information that can identify the participant.

The phone number in the .csv dataset will be replaced by the Research ID when the data is downloaded by the Project Coordinator at the IBR.

Data from Coaches. Each Coach will need to have a caseload tracking file with participants' name, Research ID, and phone number, accessible on their TCU-owned secure laptop computers in a Master Linking file. Each laptop will be protected by a strong password and the caseload tracking file—a Microsoft Excel database—will be encrypted and protected by a strong password and used for documenting assertive referrals and other support services (e.g., assistance with obtaining clothing, housing, or transportation) for individual participants, as well as case notes on MI telehealth sessions. The tracking files maintained by Coaches will be uploaded to TCU Box on a weekly basis for the duration of the study. Downloaded caseload tracking files will be stored at the IBR on a TCU-secure computer accessible by authorized IBR researchers; tracking files will be separate from the Master Link File.

Behavioral healthcare provider data. Data requests to behavioral healthcare treatment providers will be conducted on a monthly basis. To facilitate the requests and maintain confidentiality, providers will be given a Treatment Code number (not the Research ID) at the start of the study for individuals receiving services at their agency. The Provider Data Request Form (included in the Appendix), will include only the Treatment Code; no participant name or Research ID will appear on the form or in the email requesting the data. Completed forms will be uploaded by the provider to TCU Box and available for download by authorized project staff. Data from the forms will be entered into a provider data tracking Microsoft Excel file at the IBR. The Treatment Code will be maintained in the Master Linking File that will be encrypted and stored at the IBR on a secure computer separate from any other participant data.

Participant interviews. The semi-structured interview (Individual Interview Guide is included in the Appendix) with a member of the research team will take place via meeting-specific HIPAA compliant Zoom chat or by phone. Audio recordings will be processed at the IBR. Audio files will be uploaded on password protected computers the IBR by the PI or Project Coordinator and transcribed for coding by a transcript service that we have used on multiple Federally-funded projects. Transcription files will be redacted and formatted before upload to Atlas.ti coding software. Original audio files and transcripts will be stored at the IBR on a separate secure computer, accessible only to authorized project staff.

17. Potential Benefits: Describe the potential benefits of the research to the participants, to others with similar problems, and to society.

Participation in this research may increase individuals' knowledge, self-efficacy, and skills that they can use to deal with life problems that impede successful recovery. From a larger perspective, participation may help to improve the quality of care for persons experiencing life-threatening use of opioids or other substances, and this may benefit not only the individual by reducing his/her pain and risk of overdose, but also by lessening the burden

placed on their family and society at large. A more effective intervention for supporting recovery also benefits behavioral healthcare programs by improving health outcomes thereby saving staff time and program costs. We anticipate that this research may also have important benefits for public health by reducing the risk of opioid overdose fatalities.

Participation in this intervention will provide information on the usefulness of telehealth services for changing attitudes and intentions and subsequent behavioral risks with regard to serious opioid or other substance use. We will also gain valuable information about the use of telehealth technology for delivering the intervention with individuals in recovery.

18. Training for Protecting Human Research Participants: Submit training certificates for all the study investigators. The training link is available on the TCU IRB webpage at www.research.tcu.edu.

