Recruitment will take place with clients who are recently accepted into the police Opioid Diversion Program (ODP) available in participating police agencies in Lake County, Illinois. We will coordinate with police agencies to put up an informational poster in each agency, introducing the research opportunity; length of the intervention (12 weeks); and eligibility criteria (stated in #11 above). The poster will also state that participation is voluntary , and (c) compensation for completed study activities. This same information will be included in a Recruitment Flier (see Appendix) that will be available to new ODP clients after they have completed the intake screening for the diversion program. Clients who are interested in hearing more about the study will be asked by Lake County Health Department (LCHD) staff to electronically sign a release authorizing LCHD to release the client's name and contact information to the T-CAP Research Assistant (RA). The release will be signed before ODP clients start outpatient or residential treatment, following ODP intake (screening and treatment referral). The TCU RA will contact the client a via phone to schedule a time for the virtual Informed Consent session that is convenient to the individual.

13. Consenting Procedure: Describe the consenting procedure, whether participation is completely voluntary, whether the participants can withdraw at any time without

penalty, the procedures for withdrawing, and whether an incentive (describe it) will be offered for participation. If students are used as participants, indicate an alternative in lieu of participation if course credit is provided for participation. If a vulnerable population is recruited, describe the measures that will be taken to obtain surrogate consent (e.g., cognitively impaired participants) or assent from minors and permission from parents of minors.

In T-CAP, the RA will be the only researcher who will Administer informed Consent. The RA will contact clients going into outpatient (OP) treatment by phone within 3 business

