days of the ODP intake to describe the study and answer questions. For clients who are entering residential treatment, the RA will contact the residential provider to speak to the client to describe the study and answer questions. For recruiting, we will call the residential provider phone number and ask to speak with individuals in treatment for the Opioid Diversion Program who are ready to be released from treatment. The provider will not be involved in recruiting for the study and will not have knowledge about an individual's decision to learn more about the project and plans to meet with the Research Assistant (RA) at an arranged location, once released. The RA will arrange _____ phone meetings with interested clients; within 4 days of the ODP intake for clients in OP treatment and within 4 days of discharge for clients in residential care. During the scheduled phone meeting, the RA will explain the consent process and steps to complete the virtual Consent form accessed through Qualtrics, describe the project, and answer any questions. The RA will then send the Qualtrics link to the individual's cell, tablet, or PC. Consent as well as responses to the Eligibility Questions (see Eligibility Questions in the Appendix) will be recorded via Qualtrics where participants will click on their responses for consent such as "I agree to participate" or "I do not agree to participate." The RA will confirm the consent agreement to participate in the study by reviewing the Qualtrics data, before calling back to ask if the participant has follow-up questions about the study and to describe the steps to complete baseline data collection. Participation will be completely voluntary and clients will be told that there are no legal consequences for declining participation, including having no effect on ODP status.

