Informed Consent document; an \$80 e-gift card for the time to complete intake surveys at the start of the study and \$40 e-gift cards for completing assessments at week 6 (the midpoint) and week 12 (the end of the intervention period) during the 3-month study (eligible for up to \$160) in the form of electronic gift cards to online merchants (e.g., Walmart, Amazon). Participants who use their own smartphone will get a \$25 electronic gift card each month they participate in the study for messaging and data charges (a total of \$75 for 3 months). Participants will not be responsible for any costs to participate in this study. The *Participant Interview Informed Consent* document will indicate that compensation is a \$20 electronic gift card for completing a scheduled interview with a member of the research team. Participants who volunteer to be interviewed at the end of the study will be contacted by the RA to schedule a virtual interview. Both Consent documents will also have information indicating that participation or lack of participation will not affect the individual's status in the ODP, treatment, or treatment status in any possible way. Therefore, participation will be strictly voluntary and should clients choose not to participate or withdraw from the study at a later time, they may do so without repercussion. Participants can withdraw from the study by contacting the RA or Coach by phone and stating that they wish to stop participating. In cases where the Coach is contacted, the Coach will relay the decision to the RA for administrative purposes. The Consent will explain that the research-issued smart phone equipment will be collected by the RA at a time to be arranged with the participant. The Informed Consents will also describe the confidentiality assurances and the procedures employed to safeguard the data. In particular, it will be explained that information collected will be identified only by a random participant **Research ID** number and research reports will only be in aggregate form, whereby no individual can be identified. Recorded interviews will be redacted and identified only by the Research ID for tracking purposes. No individual data (survey, agency, or recorded opinions) will be reported to the ODP authorities or any other entity. The *Primary Study Informed Consent* will include language to allow release of behavioral healthcare agency data from the substance use treatment provider (providing services as part of the Opioid Diversion Program) to the research team for tracking participants across the 12-week intervention, thus providing treatment performance indicators. The *Primary Study Informed Consent* will also state that behavioral healthcare data will be requested by the research team using a variation of the Research ID (referred to as the **Treatment Code**) to link data to a participant. The Treatment Code is an arbitrary number assigned to each participant by the research team. The Code will be provided to the behavioral healthcare provider in a file that links the Code to the participant's name. Therefore, data requests from the research team will include only the Treatment Code, which providers will use to identify the client from the linking file. Behavioral healthcare providers will use only the Treatment Code in submitting data to the research team. Behavioral agency data will be shared with the research team via upload to TCU Box, a secure online data sharing platform. After an Informed Consent has been administered, the RA will answer questions and the client will then be asked to provide written consent.

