
Study Procedures: Provide a chronological description of the procedures, tests, and interventions that will be implemented during the course of the study. Indicate the number of visits, length of each visit, and the time it would take to undergo the

various tests, procedures, and interventions. If blood or tissue is to be collected, indicate exactly how much in simple terms. Flow diagrams may be used to clarify complex projects.

Research ID. After participants have electronically consented to participate on an Informed Consent document, they will receive the Qualtrics link to complete the Demographic Forms, and Contact Information Forms. Each participant, will then be assigned a Research ID that will be the only identification used on any project data. Because study participants are referred by the Diversion program to distinctly different forms of treatment (either outpatient or residential), the Research ID's will be based on two separate 3-digit series; 100 for participants in outpatient and 200 for participants released from residential. The Research ID will be written on the signed Informed Consent and entered into a Master Link File that will pair the participant name with the Research ID. This file will be kept on password protected laptops used by the RA and Coaches and password protected computers used by the PI and Project Coordinator at the IBR.

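### Aim 2 gives initiation and retention no time origin or index episode, although residential participants join around discharge from the stay they were referred to

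*Combined protocol and SAP*

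**What the plan says.** **Outcomes and their use.** Section 14, Aim 2 names initiation of in-person substance use (SU) treatment, short-term retention in the SU treatment to which the client was referred, and access to other services. It compares completers (C, all seven video calls) with non-completers (NC) by t-tests and chi-square tests. The resulting effect sizes are to inform the sample size of a future R01. The baseline C-vs-NC checks named are demographic characteristics and opioid use frequency and amount.

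**When participants join.** Under Section 12, screening and treatment referral take place at intake to the Opioid Diversion Program (ODP). Section 13 then has the research assistant (RA) hold the study meeting "within 4 days of the ODP intake for clients in OP treatment and within 4 days of discharge for clients in residential care". In residential facilities the RA asks for "individuals in treatment for the Opioid Diversion Program who are ready to be released from treatment", and the same section refers to the client's "plans to meet with the Research Assistant (RA) at an arranged location, once released". The Coach's first text comes after the baseline surveys (Study Procedures, Baseline Survey Administration).

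**Setting.** The Research ID paragraph of Study Procedures recognises outpatient and residential treatment as clearly different and assigns ID series of "100 for participants in outpatient and 200 for participants released from residential". It uses the distinction only for numbering.

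**Data.** The monthly Provider Data Request Form (Study Procedures, Agency Records) collects level of care, program length, initiation and discharge dates, and sessions scheduled and missed. Section 13 describes the agency data as being "for tracking participants across the 12-week intervention, thus providing treatment performance indicators".

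**The concern.** Aim 2 is meant to show how well these measures gauge the impact of telehealth. That requires outcomes that are still open when the Coach first makes contact. For a residential participant, the ODP-referred stay began before consent and is over or nearly over by then. If it is scored, the participant counts as initiated and retained whatever T-CAP does.

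Two things are at stake for the R01 effect sizes. Fixed outcomes shrink the C-vs-NC difference. And if residential participants are more or less likely than outpatients to complete seven calls, setting alone can produce a difference. The named baseline checks would not reveal this, because setting is not among them. Both problems come on top of the self-selection already present in any C-vs-NC comparison.

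**Working it through.** The plan gives no rate, residential share, C/NC split or power figure, so there is no stated result to reproduce. The check is first a reading of the timeline, then an illustration on assumed inputs.

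**1. Timeline**

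| | Outpatient (100 series) | Residential (200 series) |
|---|---|---|
| Treatment referral | ODP intake | ODP intake |
| RA meeting | within 4 days of intake | within 4 days of discharge |
| Referred episode at consent | may or may not have started | started; over or nearly over |
| First Coach contact | after baseline surveys | after baseline surveys |

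The discharge window does not say before or after, but the wording about release in Section 13 and the Research ID paragraph points to after. Even if the meeting came before, at most 4 days of the stay would remain.

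**2. What a literal analyst could do.** Section 14 speaks of referred treatment, and the provider form has an initiation date. Taking both at face value, the residential stay is scored and every 200-series participant is initiated (score 1). An analyst who keeps that stay as the index episode but counts only events after consent would score 0. Nothing in Section 14 decides between these, or in favour of counting later care.

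**3. Dilution.** Let f be the residential share, equal in C and NC, with every residential participant given the same score. Then pooled risk difference = (1 - f) x outpatient risk difference. With f assumed at 20% to 50% (8 to 20 of 40), the factor is 0.80 to 0.50. This holds for risk differences only. With assumed outpatient initiation of 80% (C) vs 50% (NC) and residential scored 1:
- f = 20%: 84% vs 60%. Cohen's h keeps 85% of its outpatient value and the log odds ratio 90%.
- f = 50%: 90% vs 75%. Cohen's h keeps 63% and the log odds ratio 79%.

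Section 14 does not say which effect-size scale will be used.

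**4. Confounding by setting.** Suppose outpatient initiation p is the same in C and NC, so there is no true difference. With residential scored 1, spurious difference = (f_C - f_NC)(1 - p). For shares differing by 10 to 30 points and p from 90% down to 50%, this is 0.1 x 0.1 = 1 point up to 0.3 x 0.5 = 15 points, in either direction. With residential scored 0 it is -(f_C - f_NC)p. Example with p = 60%, f_C = 50%, f_NC = 30%:
- Scored 1: 0.2 x 0.4 = +8 points (80% vs 72%).
- Scored 0: -0.2 x 0.6 = -12 points (30% vs 42%).

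The scoring choice alone reverses the sign.

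**5. What it could do to a planned sample size.** Two-sided 5%, 80% power, 1:1, on the same assumed 80% vs 50%:
- Outpatients only: difference 0.30, 39 per arm.
- f = 25%: difference 0.225; 59 per arm (scored 1) or 77 (scored 0).
- f = 50%: difference 0.15; 100 per arm (scored 1) or 152 (scored 0).

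**6. Precision when outcomes are split by setting.** 95% half-width = 1.96 x sqrt(0.24/n1 + 0.24/n2), at an assumed rate of 60% (0.6 x 0.4 = 0.24). This Wald formula is rough at these sizes. Outpatients only, none started before consent:
- Even C/NC split: f = 20% gives 16 per group, 34 points; f = 50% gives 10 per group, 43 points.
- 30/10 split: f = 20% gives 24 vs 8, 39 points; f = 50% gives 15 vs 5, 50 points.

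If some outpatients started before consent and are reported separately, the even-split figures rise to 39-50 points (a quarter started early) or 48-61 points (half did).

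**The case against.** The best defence is that care after consent was always intended. Agency data are for tracking across the 12-week intervention. The T-CAP Intervention paragraph gives the Coach a role after treatment ends. Provider forms are requested for participants receiving services at the agency, which a discharged client may no longer be doing. This makes post-consent care a plausible intent, and it stands to that extent. It does not settle the matter: these passages describe a data window, a service role and a request procedure. One agency may also supply both residential and later care.

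A reader might infer that the plan pools the two settings or scores the residential stay. The documents do not support that. Pooling is only the default reading of a section that is silent on setting, the list of baseline checks is open-ended, and the appendices with the survey batteries and provider form were not available. Section 13 also speaks of clients entering residential treatment, although its recruiting call and meeting window are tied to release.

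A reader might also take the 80-50% factor as the expected loss. It is not: every input is assumed, and the factor applies to risk differences only.

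Finally, the illustrated spurious differences of 1-15 points are smaller than the sampling error of a pooled comparison of 40 people: a half-width of about 30 points at 20/20 or 35 at 30/10, at a 60% rate. That is true, and it limits the severity for a feasibility study. It does not make an undefined outcome acceptable in a study whose second aim is to evaluate its measures.

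**Conclusion.** The concern holds in a limited form. Section 14 gives initiation and retention no time origin or index episode and takes no account of setting. For residential participants, the ODP-referred stay begins, and is nearly or fully complete, before Coach contact. If that stay is scored, as the wording allows, those participants tell us nothing about T-CAP, and the C-vs-NC effect size can be diluted or confounded by setting. If later care is scored, the outcomes can still respond to T-CAP, but the plan does not say that this is the rule.

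The size cannot be determined from the documents, and the figures above show only what assumed shares and rates would do. Severity is minor to should-fix: the study is small and developmental, but the effect sizes are meant to be carried forward and the correction is cheap.

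**What to change.** In Section 14, Aim 2:

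1. Count initiation and retention only from electronic consent to week 12. For the 200 series, state that the index episode is SU care after residential discharge. Report separately anyone, in either series, who is already in SU treatment at consent. Note that a short gap remains between consent and first Coach contact, so a start in that gap would still count.
2. Report each Aim 2 outcome by 100/200 series, and add setting to the baseline C-vs-NC comparison.
3. Label any pooled C-vs-NC effect size as descriptive and not a treatment effect. The seventh call falls in week 12, so completer status is settled over the same period as the outcomes, and a consent-based origin does not remove that overlap.

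Base retention on what the provider form collects: initiation and discharge dates and monthly scheduled and missed sessions. A rule for gaps in attendance or a days-available denominator is not needed, and the monthly form, which lists no session dates, would not support a fine-grained gap rule.

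**Cost.** This is mainly a change of wording, since setting, level of care and dates are already collected. The downsides are small cells, with half-widths of about 34-50 points for an outpatient difference under the assumptions above and wider if some started before consent, and incomplete agency data. The consent to release records names the provider serving the ODP, and a memorandum of understanding with the provider is required, so care after discharge at another provider may rest on self-report.
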